## 4 STUDY PROTOCOL

### 4.1 Study Objective

We propose a pilot randomized controlled trial to evaluate antihypertensive treatment among PLWH with pre-HTN at GHESKIO. This study will provide critical data on the feasibility, benefits and risks of antihypertensive treatment for CVD prevention among PLWH with pre-HTN that will inform a future definitive trial powered for incident CVD events. For the pilot study, we will enroll 250 PLWH (18-65 years of age) who have been on ART for  $\geq 1$  years with viral suppression within past 12 months and SBP 120-139 or DBP 80-89 mm Hg and no current antihypertensive treatment; randomize them to “early HTN treatment” or the current standard of care (SOC); and follow them for 12 months.

Amlodipine is the recommended first-line anti-hypertensive medication according to Haiti’s new primary care HTN guidelines. Participants in the early HTN treatment arm will initiate amlodipine 5 mg immediately, increasing to 10 mg if SBP  $>130$  mm Hg after 1 month. Participants in the SOC arm will initiate amlodipine only if they develop HTN (SBP  $\geq 140$  or DBP  $\geq 90$  mm Hg). We hypothesize that early HTN treatment will not impact viral suppression and be feasible and safe, with a reduction in BP at 12 months compared to SOC. The primary aim is to assess the feasibility of initiating antihypertensive treatment among PLWH with pre-HTN through a pilot randomized controlled trial comparing early HTN treatment to SOC. Feasibility outcomes include enrollment and retention data, proportion who initiate amlodipine, and incremental change in SBP at 12 months between arms. The secondary aim includes analyzing the following measures: viral suppression, HIV medication adherence, adverse events, acceptability, CVD risk profile, and pre-existing myocardial and vascular dysfunction.

### 4.2 Study Site

The trial will be conducted at the GHEKSIO Centers in Port au Prince, Haiti.

### 4.3 Study Population

The study population will include 250 PLWH from GHESKIO’s HIV clinic. Inclusion and exclusion criteria are in Table 3. We included younger PLWH given the early onset of HTN in Haiti and limited the upper age to 65 years given the low incidence of HIV above this age. We exclude PLWH with kidney disease ( $<60$ mL/min/1.73m $^2$  using CKD-Epi equation) because Haiti’s guidelines recommend furosemide as first-line treatment for this group. We exclude diabetics (defined as fasting glucose  $\geq 126$  mg/dL or non-fasting glucose  $\geq 200$  mg/dL, or taking diabetes medications) because Haiti’s guidelines recommend initiation of antihypertensive medications when SBP  $\geq 130$  mmHg or DBP  $\geq 80$  mmHg. Individuals on a protease inhibitor with ritonavir will be excluded as ritonavir can increase levels of amlodipine. Women who become pregnant will be censored at time of pregnancy.

**Table 3. Inclusion and exclusion criteria for the trial**

Inclusion criteria	Exclusion criteria

 
• PLWH 18-65 year of age
 
• ART duration <math>\geq 1</math> year, stable regimen <math>\geq 6</math> months
 
• HIV 1-RNA <math>< 1,000</math> copies/mL within past 12 months
 
• Pre-HTN (SBP 120-139 or DBP 80-89 mm Hg)
 
• No current antihypertensive treatment
 
• Receives HIV care at GHESKIO
 
• Willing to provide consent
 
	
 
• Pregnancy
 
• Kidney disease or diabetes
 
• Protease inhibitor/ritonavir
 
• Advanced illness with limited life expectancy
 
• Plans to move out of the area within the next year
 
• Clinician determination that patient is unstable on ART
 

#### **4.4 Recruitment and Informed Consent**

Screening and recruitment will follow GHESKIO Clinical Trials Unit procedures that have been highly successful in NIH trials. We will identify and invite potential participants both 1) in-person at GHESKIO's HIV clinics using real time BP measurements and 2) from GHESKIO's electronic medical record (EMR) using BP measurements in the past 12 months, age, ART duration, viral suppression, and no current antihypertensive treatment. PLWH meeting these eligibility criteria will be tagged in the EMR as participants for recruitment and a list will be given to the study team.

The research nurse will approach patients in the HIV clinics, or call PLWH on the list to introduce the study and invite interested individuals for informed consent and then a screening visit. After confirming basic eligibility criteria, the research nurse will initiate informed consent procedures among eligible participants. The informed consent process consists of two education sessions, followed by assessment of understanding and written informed consent.

After informed consent, participants will be assigned a unique study ID number and undergo a screening visit with review of eligibility criteria and screening labs. Pre-HTN is defined as  $\geq 2$  BP measurements of SBP 120-139 mm Hg or DBP 80-89 mm Hg on separate days. All BP measurements will be done according to AHA/WHO guidelines. Screening labs will be collected (urine or serum pregnancy test, fasting or random glucose, and creatinine) to evaluate if the patient is pregnant, has diabetes, or kidney disease. We will document the number screened and reasons for study exclusion.

In 2018, 18,872 PLWH on ART received care at GHESKIO with mean duration of ART of 5.6 years, 76% on first-line regimens, 86% virally suppressed, and median age of 35 years. We estimate 3,819 PLWH at GHESKIO satisfy the eligibility criteria. Based on our past enrollment experience, we are confident 250 participants can be enrolled from this sampling frame in 6 months.

#### **4.5 Study Enrollment**

Participants that meet study eligibility criteria will proceed to study enrollment visit (~90 min). Participants will be randomized to early HTN treatment vs. SOC in a 1:1 ratio using a computer-generated random assignment. The research nurse will collect demographic and clinical data, administer a baseline questionnaire, measure unobserved BP, and perform an ECG. The questionnaire includes a CVD medical history, family history, medications, CVD health behaviors (smoking, alcohol, physical activity, and diet) using validated questions that have been used at GHESKIO and are comparable to those used in US cohorts. Enrollment labs (~15ml of venous blood) including HgbA1c, total cholesterol, HDL, CD4 and HIV viral load (unless available from EMR in the past 6 months) will be collected. Samples of serum and plasma will be stored for future studies, with documented consent from participants. The study physician will interpret the ECG and perform an echocardiogram and vascular ultrasound.

Study drug will be dispensed to participants randomized to the early treatment arm with appropriate education and counseling on adherence and potential side effects. Amlodipine will be started at 5mg at

enrollment and increased to 10mg if SBP  $>130$  mm Hg after 1 month for participants in the early treatment arm. Locator and contact information will be verified and follow up appointment given.

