HIV is associated with equal, if not greater, CVD risk as diabetes; yet, the WHO still recommends PLWH initiate antihypertensive treatment at the same BP threshold as adults without HIV. Data are needed to clarify if initiation of antihypertensive treatment among PLWH with pre-HTN can prevent progression to HTN, and ultimately CVD-related mortality. The proposed pilot trial is the first step to explore the feasibility, benefits, and risks of initiating antihypertensive treatment among PLWH with pre-HTN in a well-established HIV program in Haiti, one of the poorest countries in the world. Knowledge gaps include: Is it feasible to initiate and integrate antihypertensive treatment into HIV care among relatively healthy PLWH with pre-HTN? Could initiating antihypertensive treatment worsen HIV outcomes? What is the BP reduction using amlodipine (which is Haiti's first-line antihypertensive medication) among PLWH with pre-HTN? Data from this pilot trial will inform the design of a future multicenter trial powered for incident CVD events. **Our goal is to change guidelines** to lower the BP threshold for initiation of antihypertensive medications among PLWH, should earlier HTN treatment prevent CVD.

Table 2: Summary of WHO and Haitian HTN definitions and guidelines		
Category	Definition	Threshold for initiation of antihypertension treatment
Normal	SBP < 120 and DBP < 80	
Pre-HTN	SBP 120-139 or DBP 80-89	Diabetes & Chronic Kidney Disease (at SBP $\geq$ 130 or DBP $\geq$ 90)
HTN	SBP $>$ 140 or DBP $>$ 90	General adults including PLWH

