**Table 4: Study Measures and Schedule**

Required forms:	SCREEN	ENROLL	M1	M2	M3	M5	M6	M8	M9	M12
Screening Eligibility Form: inclusion criteria, exclusion criteria	X									
Screening Labs: urine/serum pregnancy test, fasting or random glucose, Creatinine	X									
Individual Characteristics										
Locator information: address and cell phone, friend/family member's cell phone		X	X	X	X	X	X	X	X	X
Sociodemographics: age, sex		X								
Socioeconomic factors: income, education, occupation, marital status, children.		X								
Medical History: history of CVD risk factors, CVD, HIV, tuberculosis		X								
Family History: stroke or MI in parents and 4 oldest siblings		X								
Health behaviors: current cigarette smoking,  alcohol  , physical activity 		X								X
Multidimensional Poverty: child death, educational attainment, household construction materials, possessions		X								
Clinical Measures										
Physiologic: height, weight		X								

Blood pressure in community		X		X		X		X		
Blood pressure at clinic		X	X		X		X		X	X
ECG		X								
Echocardiography and vascular ultrasound		X								
Enrollment Labs: HgbA1c, total cholesterol, HDL, CD4, VL		X								
12M Labs: VL										X
Medical record abstraction: diagnoses codes (ICD-9), laboratory measures, diagnostic imaging, and cause of death among participants who receive clinical care from the GHESKIO NCD clinic, a GHESKIO-affiliated hospital, or other health facility			X	X	X	X	X	X	X	X
Clinical Management										
Medication Adherence		X	X	X	X	X	X	X	X	X
Medical record abstraction for development of HTN after enrollment			X	X	X	X	X	X	X	X
Medical record abstraction for clinical management of CVD risk factors: smoking, HLD, DM		X	X	X	X	X	X	X	X	X
Intervention related										
Amlodipine initiation form		X								
In depth interviews about feasibility, acceptability				X	X	X	X	X	X	X
Adverse Events				X	X	X	X	X	X	X

**BP measurement:** All BP measurements will follow AHA/WHO guidelines using semi-automated electronic cuffs (OMRON 742-5 series at home and HEM907 in clinic) of 3 BPs separated by  $\geq 1$  minute with the individual seated at rest. The average of the 3 BPs is the BP for the visit.

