**Aim 2:** The proportion of participants in each study arm with viral suppression (HIV-1 RNA < 1000 copies/mL) at 12 months will be compared between study arms using the Fisher exact test; we assume participants who are lost to follow-up or dead at 12 months will have HIV-1 RNA > 1000 copies/mL. Other categorical data including medication adherence, CVD risk factors (e.g. diabetes) will be analyzed similarly. Longitudinal data such as BMI and adherence (continuous or binary/categorical) will be analyzed accounting for repeated measures within participants, via LMM and GLMM as described above. We will also consider Generalized estimating equation-based method (so called, marginal or population-averaged model) and will report consistency or meaningful discrepancy. Acceptability will be assessed in qualitative interviews by [name] who is trained in qualitative research using interview information transcribed verbatim, translated into English, and then coded for analysis using a thematic coding scheme. We will also describe adverse events among all participants.

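### HbA1c is first drawn at the randomization visit, so a standard-of-care participant who passed the glucose screen can be held to the 140/90 rule yet referred to care with a lower diabetic threshold

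*Combined protocol and SAP*

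**What the plan says.** Table 3 lists "Kidney disease or diabetes" as an exclusion. Section 4.3 gives the reason for excluding diabetes: Haiti's "guidelines recommend initiation of antihypertensive medications when SBP" is at least 130 mm Hg or DBP at least 80 mm Hg. That range overlaps the trial's entry range of SBP 120-139 or DBP 80-89.

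The definition used for the exclusion is also in 4.3: "We exclude diabetics (defined as fasting glucose" of at least 126 mg/dL, non-fasting glucose of at least 200 mg/dL, or use of diabetes medication. Section 4.4 and the screening row of Table 4 match it: "urine/serum pregnancy test, fasting or random glucose, Creatinine". HbA1c is not among the screening tests.

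HbA1c comes in at section 4.5, among the "Enrollment labs (~15ml of venous blood) including HgbA1c, total cholesterol, HDL, CD4 and HIV viral load". Table 4 marks it only in the enrollment column. At the same visit participants are randomized 1:1 and early-arm drug is dispensed. Table 5 then classifies diabetes as HbA1c above 7 or on medication.

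For the comparator, section 4.1 states: "Participants in the SOC arm will initiate amlodipine only if they develop HTN", meaning SBP of at least 140 or DBP of at least 90. Section 4.6 repeats this, and 4.7 adds that two measurements on different days are needed. None of the three makes an exception for diabetes.

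Section 3.2 uses an elevated HbA1c as an example of a finding that leads to referral, and says the site's non-communicable disease unit manages hypertension and diabetes by national guidelines. Section 4.7 says those clinicians are independent of the research team.

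**The concern.** The exclusion exists to keep out people whose guideline treatment threshold differs from the one the SOC arm tests. It is applied with one definition of diabetes before randomization, while a second definition is applied to blood drawn at the randomization visit. Someone can be non-diabetic for eligibility and diabetic for the baseline risk profile.

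If that person is in the SOC arm and in the overlapping blood pressure range, there are two outcomes. They may stay off amlodipine under the trial rule although the guideline cited in 4.3 would start treatment. Or the referral clinic may start it below 140/90, outside the SOC rule. Section 4.7 describes the initiation threshold as the sole difference between arms, so such starts touch the one contrast the trial has. Section 4.3 says what happens when pregnancy arises after randomization (censoring). No section does the same for diabetes.

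**Working it through.** **1. Order of events.** Screening visit: glucose, creatinine, pregnancy test (4.4, Table 4). Enrollment visit: randomization, HbA1c draw, first dispensing in the early arm (4.5, Table 4). HbA1c is therefore not an eligibility test. Section 4.5 lets the laboratory work be skipped when a result from the past 6 months is in the medical record. If that covers HbA1c as well as viral load, some values are known earlier, but they still do not decide eligibility.

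**2. Who falls in the gap.** Untreated participants below the glucose cut-offs with HbA1c above 7. Diabetics detected by glucose or by medication are already excluded.

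**3. Where the rules differ.** The SOC rule (140/90) and the two statements of the diabetic threshold, applied to each blood pressure band allowed at entry:

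| Band (mm Hg) | SOC rule | Section 4.3 (130 or 80) | Table 2 (130 or 90) | Conflict? |
|---|---|---|---|---|
| SBP 120-129, DBP <80 | no start | no start | no start | none at that reading |
| SBP <130, DBP 80-89 | no start | start | no start | only under 4.3 |
| SBP 130-139, DBP <90 | no start | start | start | yes, under both |

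The middle row turns on a discrepancy inside the document. Table 2 gives DBP of at least 90 for "Diabetes & Chronic Kidney Disease", and 4.3 gives at least 80 for diabetes.

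**4. How many.** The documents give no share p of glucose-negative participants with HbA1c above 7. I assume 1% to 4%. With 250/2 = 125 in the SOC arm:
- expected number = 125 × p = 1.25 at 1% and 5 at 4%;
- chance of at least one = 1 − (1 − p)^125 = 72% at 1% and 99% at 4%.

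Both are upper bounds for a conflict, because they count every such participant whatever the blood pressure. The documents do not give the share in the conflicting bands.

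**5. Effect on the primary comparison.** Section 4.9 states 80% power at two-sided alpha 0.05 (two-sidedness assumed) for 4 mm Hg with 250 participants. It gives no SD, so that figure cannot be reproduced independently, only calibrated to. With 6 time points and correlation 0.95 the variance factor is (1 + 5 × 0.95)/6 = 0.958. The implied SD is 4/(1.96 + 0.84) × √(125/2)/√0.958 ≈ 11.5 mm Hg.

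Take the worst case, in which every affected SOC participant is treated early and gets the full effect. The difference becomes 4 × (1 − p), and power is Φ(2.80 × (1 − p) − 1.96):

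| Assumed p | SOC participants | Difference (mm Hg) | Power |
|---|---|---|---|
| 0 | 0 | 4.00 | 80% |
| 1% | 1.25 | 3.96 | 79% |
| 2% | 2.5 | 3.92 | 78% |
| 4% | 5 | 3.84 | 77% |
| 5% | 6.25 | 3.80 | 76% |
| 10% | 12.5 | 3.60 | 71% |

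**The case against.** The strongest reply is that this is an unaddressed edge case. Much of that stands.

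- **Screening exists.** A reader might infer that diabetics enter the trial unscreened. They do not: glucose and medication are checked before randomization.
- **No direct counter-instruction.** A reader might infer that the protocol orders amlodipine for a diabetic SOC participant at SBP 130. It does not. Section 4.3 explains an exclusion, Table 2 summarizes external guidelines, and the sentence in 4.7 about diabetics names a drug and not a threshold. The lower threshold reaches the participant only through referral (3.2 and 4.7).
- **Not every case conflicts.** The table of bands shows that a raised HbA1c alone is not enough.
- **Expectation of diabetics.** Section 4.9 says "Other categorical data including medication adherence, CVD risk factors (e.g. diabetes) will be analyzed similarly", and the Protocol Summary lists diabetes in the enrollment risk profile. These may be generic lists. Table 5 also lists hypertension treatment, which is excluded at entry. They do not show that the plan expects diabetics among those randomized.
- **Post-randomization removal.** The plan nowhere proposes removing such participants, so bias from doing so cannot be charged to it.
- **Partial handling.** Table 4 schedules record abstraction on diabetes management, and 4.9 plans per-protocol and changepoint sensitivity analyses. The changepoint analysis is for SOC treatment initiation. As described, neither separates a start at 140/90 from one prompted by a diabetes diagnosis.

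These points limit the size of the problem. They do not supply a rule for the participant in the gap, and they do not explain why the exclusion and the baseline classification use different definitions.

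**Conclusion.** The point holds as a limited gap in the design. The text alone establishes the two diabetes definitions, the timing of HbA1c, the missing rule for diabetes found after randomization, and the discrepancy in the diastolic threshold. No assumed figure is needed for any of these.

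The size rests on an assumption. At 1-4%, at most about 1 to 5 of 125 SOC participants are affected, fewer once blood pressure band is counted, and the worst-case loss of power is 1 to 3 percentage points. A reader might infer a material threat to the primary endpoint, but these figures do not support that. What is at stake is how a few participants are managed and whether SOC starts follow the trial's rule. Because the remedy uses a test already planned for everyone, it is worth making.

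**What to change.** 1. Move HbA1c from the enrollment to the screening laboratory tests in 4.4, 4.5 and Table 4, so that the result is known before randomization.
2. Reconcile the diabetes definitions in 4.3 and Table 5 so that one governs both eligibility and baseline description, and carry it into Table 3.
3. Reconcile the diastolic threshold for diabetics between Table 2 and 4.3.
4. Reconcile the SOC initiation wording (4.1, 4.6, 4.7) with the referral text (3.2, 4.7) for diabetes found after randomization, and state how such participants are followed and analyzed. Earlier HbA1c testing does not cover diabetes that arises during follow-up, so this is needed in any case. Which threshold applies is for the investigators to settle.
5. Record the reason for each SOC amlodipine start, so that the changepoint and per-protocol analyses in 4.9 can separate these starts.

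The cost is HbA1c testing in people who fail screening (the documents do not give the number to be screened) and waiting for the result before randomization. The test is already planned for all 250 participants. If the agreed definition leads to a few more exclusions, the estimated pool of 3,819 eligible patients in 4.4 can absorb them. Items 2 to 5 need wording and one data field.

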## Protocol Summary

**Title:** Prehypertension in Haiti

**Study Summary:** We propose an unblinded pilot RCT of 250 persons living with HIV (PLWH), aged 18-65 years, who receive ART care at GHESKIO, are virally suppressed, and have pre-HTN (SBP 120-139 or DBP 80-89 mm Hg) to be randomized to **early HTN treatment** versus **standard of care** (SOC). Participants will be recruited from GHESKIO's HIV clinic. Eligible individuals will complete informed consent and be randomized to early HTN treatment vs. SOC. Participants in early HTN treatment will initiate amlodipine immediately versus those in SOC will initiate amlodipine only if they meet the HTN threshold during the study period. All participants will be followed for 12 months. The primary outcome is mean change in SBP at 12 months between study arms. Secondary outcomes are viral suppression, medication adherence, adverse events, and acceptability. We will also assess CVD risk factors and myocardial/vascular dysfunction among all participants at enrollment.

**Population:** We will recruit 250 PLWH from GHESKIO'S HIV Clinic. Inclusion criteria: PLWH 18-65 years of age, ART duration  $\geq$  1 year , stable regimen  $\geq$  6 months, HIV 1-RNA  $<$  1,000 copies/mL within past 12 months, Pre-HTN (SBP 120-139 or DBP 80-89 mm Hg), no current antihypertensive treatment, receives HIV care at GHESKIO, and willing to provide consent. Exclusion criteria: pregnancy, kidney disease, diabetes, advanced illness with limited life expectancy, plans to move out of the area within the next year, and clinician determination that patient is unstable on ART.

**Number of Sites:** Single site: GHESKIO Center Port au Prince, Haiti

**Study Duration:** 2 years

**Subject Duration:** 12 months

**Primary Aim:** To assess the feasibility of initiating antihypertensive treatment among PLWH with pre-HTN through a pilot randomized controlled trial comparing early HTN treatment to SOC. Feasibility outcomes include enrollment and retention data, proportion who initiate amlodipine, and incremental change in SBP at 12 months between arms. The pilot trial has  $\geq$ 80% power to detect differences in change in SBP  $\geq$  4 mm Hg.

**Secondary Aims:** To also examine the following outcomes and measures:

- a. Viral suppression compared between study arms at 12 months (defined as HIV-1 RNA  $<$  1000 copies/ml)

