**HIV services for all participants:** Provision of HIV services, including ART, adhere to national guidelines. The first-line ART regimen is TDF/3TC/dolutegravir; second-line regimens include protease inhibitors. Patients who are virally suppressed are seen in the GHESKIO HIV clinic every 6 months for adherence assessment and medication refills. HIV-1 RNA viral load is measured annually. BP is measured at every clinic visit.

**Early HTN treatment vs. SOC procedures:** The only difference between study arms is the BP threshold at which amlodipine is initiated. Participants in the early HTN treatment arm will initiate amlodipine 5 mg immediately followed by an increase to 10 mg if SBP  $>130$  mm Hg after 1 month or more. Participants in the SOC arm will initiate the same algorithm but at the standard BP threshold for HTN which is SBP  $\geq 140$  or DBP  $\geq 90$  mm Hg in two measurements on different days. There are no known drug-drug interactions between the first-line ART and amlodipine. Haiti's guidelines recommend amlodipine as the first line regimen for diabetic individuals as well.

**Clinical management of CVD risk factors and diseases:** Any participant diagnosed with a risk factor or disease through study procedures will be escorted to the GHESKIO clinic or affiliated hospital in Port-au-Prince for clinical care and further evaluation by clinicians who are independent of the research team (see Human Subjects). Clinical care is provided free of charge.

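### The 12-month viral suppression comparison ignores the enrollment viral load, so viremia that pre-dates amlodipine and persists is counted as failure, at a cost in precision and sensitivity to harm

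*Combined protocol and SAP*

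**What the plan says.** **Eligibility.** The Protocol Summary and Table 3 require HIV-1 RNA below "1,000 copies/mL within past 12 months". Section 4.1 likewise speaks of "viral suppression within past 12 months".

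**Screening.** No viral load is drawn. Section 4.4 reads: "Screening labs will be collected (urine or serum pregnancy test, fasting or random glucose, and creatinine". Table 4 lists the same three tests.

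**Enrollment.** Section 4.5 says "Participants that meet study eligibility criteria will proceed to study enrollment visit", so eligibility is settled before that visit. At the visit, "CD4 and HIV viral load (unless available from EMR in the past 6 months) will be collected". No section says what follows if the value is 1,000 or higher.

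**Routine care.** Under the HIV services text that follows Table 4, "HIV-1 RNA viral load is measured annually".

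**Hypothesis.** Section 4.1: "We hypothesize that early HTN treatment will not impact viral suppression".

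**Analysis.** In section 4.9, Aim 2, the proportion suppressed (below 1000 "copies/mL) at 12 months will be compared between study arms using the Fisher exact test"). Participants who are lost or dead at 12 months count as unsuppressed. The only provision for adjusting imbalanced baseline variables stands under Aim 1, in the text on the SBP model. Table 5 lists viral load among the other CVD factors at enrollment.

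**The concern.** The suppression comparison is there to show whether adding amlodipine harms HIV control. The event of interest is loss of suppression after randomization. As written, the 12-month endpoint mixes that event with viremia already present at entry.

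Three things follow. Events unrelated to treatment add variance. With few failures expected, a chance difference between arms in baseline viremia can move the 12-month difference noticeably. And a real increase in rebound is diluted, which makes a non-significant Fisher result easier to obtain. For a harm question, that is the falsely reassuring direction.

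The plan does re-test participants whose last value is more than 6 months old, so it already treats such a value as too old for a baseline. It then leaves the result out of the one comparison where it matters most.

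**Working it through.** **The plan's own figure.** The only power statement (80% for a 4 mm Hg difference in SBP change, section 4.9) does not concern viral load. It also cannot be reproduced, because no SD is given. There is no power or precision figure for suppression to check.

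**Inputs from the documents.** 250 participants randomized 1:1, so 125 per arm; failure at 12 months is HIV-1 RNA at or above 1000, lost, or dead; 98% retention in past trials (section 4.6).

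**Assumptions, not in the documents.** New rebound over 12 months in those suppressed at entry: r = 5%. Share of those viremic at entry who are still viremic at month 12: k = 40-60%. Share viremic at entry, b: if rebound runs at 5% a year and qualifying results are on average 6 months old, b is about 5% × 6/12 = 2.5%; if every result were a full 12 months old, b would be about 5%.

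**Formulas**
- Failure risk: p = b·k + (1−b)·r
- Share of failures that pre-date treatment: b·k / p
- Share of outcome variance removed by stratifying: b(1−b)(k−r)² / [p(1−p)]

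| b | k | p | Pre-dating share | Variance removed |
|---|---|---|---|---|
| 2.5% | 40% | 0.0100 + 0.04875 = 0.0588 | 17% | 0.00299 / 0.0553 = 5% |
| 2.5% | 60% | 0.0150 + 0.04875 = 0.0638 | 24% | 0.00737 / 0.0597 = 12% |
| 5% | 40% | 0.0200 + 0.0475 = 0.0675 | 30% | 0.00582 / 0.0629 = 9% |
| 5% | 60% | 0.0300 + 0.0475 = 0.0775 | 39% | 0.01437 / 0.0715 = 20% |

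Confidence-interval width scales with the square root of the variance, so removing 5-20% narrows the interval by about 3-11% (1 − √0.95 to 1 − √0.80).

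**Chance imbalance.** The 95% range of the arm difference in baseline viremia is ±1.96·√[2b(1−b)/125]: ±3.9 points at b = 2.5% and ±5.4 points at b = 5%. Multiplied by the gap in failure risk (k − r = 0.35 to 0.55), this moves the 12-month difference by ±1.4 to ±2.1 points and by ±1.9 to ±3.0 points respectively.

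**Dilution.** Take an assumed 5% versus 15% failure among those suppressed at entry, with half of those viremic at entry still viremic at month 12. The exact power of the two-sided Fisher test is 70% with no viremia at entry, 65% at b = 2% and 57% at b = 5%. The risk difference shrinks from 10.0 to 9.8 and 9.5 points. With error-free knowledge of entry status, restricting to those suppressed gives 68% and 67%.

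**What reduces the gain.** Suppose the 6-month record exception hides half of those viremic at entry among participants classed as suppressed. This is pessimistic, because recent values have had less time to go out of date. The viremic stratum is then b/2, and the failure risk in the other stratum is [(b/2)·k + (1−b)·r] / (1 − b/2). Variance removed falls to 3-6% at b = 2.5% and 5-10% at b = 5%. Counting 2% lost as failures as well, p becomes 0.02 + 0.98p and the between-stratum term is multiplied by 0.98². The gain is then 2-5% and 3-8%.

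**The case against.** **No bias.** Allocation is random, so viremia at entry is balanced in expectation, and comparing 12-month suppression in all randomized participants is valid. This stands. A reader might infer that the comparison is biased; the design does not support that. The issue is precision, chance imbalance and dilution.

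**The value is not wholly unused.** A reader might infer that the enrollment viral load is ignored throughout. Table 5 lists it as a CVD factor, and sections 4.9 and the Protocol Summary compare CVD risk factors between arms, so an imbalance may become visible. This stands, but seeing an imbalance is not the same as accounting for it in the suppression comparison.

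**Not everyone viremic at entry fails.** Those who re-suppress by month 12 count as successes. Only those still viremic, lost or dead count as failures. This stands and is built into k.

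**The size could be small.** A reader might take the clinic-wide unsuppressed share in section 4.4 (100% − 86% = 14%) as the rate at entry. That figure describes all patients on ART at the clinic. The trial requires a suppressed value, at least 1 year on ART and at least 6 months on a stable regimen, and excludes patients whom a clinician judges unstable on ART. An assumed 5% yearly rebound also implies 2.5-5% at entry, not 14%.

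**Baseline status is imperfect.** Where the record holds a value from the past 6 months, no sample is drawn, and that value may be the very one that qualified the participant. A reader might infer that status at randomization is known for everyone; section 4.5 does not provide that. Stratification still uses the best value obtained before treatment and remains valid, but it recovers only part of the loss.

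**Conclusion.** The point holds as a matter of precision and interpretability. The plan accepts a viral load up to 12 months old, obtains a more recent value at enrollment for many participants, and uses that value neither for eligibility nor in the 12-month suppression comparison. Viremia that pre-dates amlodipine and persists therefore enters the endpoint in both arms.

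The documents do not allow the size to be fixed. Under the assumptions above, 17-39% of failures would pre-date treatment and stratifying would remove 5-20% of outcome variance, falling to about 2-8% with half of the viremia hidden and 2% lost. The gain in interval width is modest. The stronger reason for the change is interpretive: without it, a null Fisher result cannot separate absence of new rebound from new rebound masked by old viremia. For a secondary outcome in a pilot this is a worthwhile, low-cost improvement. It does not undermine the trial.

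**What to change.** In section 4.9, Aim 2:

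1. Add a risk difference with 95% CI for 12-month suppression, stratified by the Mantel-Haenszel method on the most recent viral load (<1000 versus ≥1000). Take that value from the enrollment visit or, under the 6-month exception, from the record. Keep all randomized participants and the rule that lost or dead participants count as unsuppressed.
2. Report by arm the proportion who lose suppression among those suppressed on that value.
3. Keep the Fisher exact test as the unadjusted result.
4. State that record values may be up to 6 months old, so some viremia at randomization will be misclassified as suppressed. Section 4.5 mentions randomization before the blood draw within the same visit, so state also that the value must pre-date the first amlodipine dose.

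The cost is analysis wording and one extra table; no new visit or sample is needed. The downside is a small viremic stratum: at 2.5-5% of 250 it would hold about 6 to 13 participants (250 × 0.025 = 6.25; 250 × 0.05 = 12.5), fewer if some are misclassified. The text should say how the estimate is reported if that stratum is empty in one arm, for example by giving the unadjusted difference with stratum counts.
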